5.2 Recruitment Methods

- **State how many subjects will be needed.**

Veteran participants:

We estimate as many as 553 - 650 veterans will be randomized.

VA employees:

We plan to interview up to 40 key stakeholders (up to 4 PCPs and 4 specialists at each site, plus interviews of stakeholders at the VISN and national level), recruited and interviewed by AAVA project staff.

- **Describe when, where, how and by whom potential subjects will be identified and recruited.**

RCT:

Recruitment and informed consent. We have been granted a waiver of documentation of informed consent and HIPAA Authorization. Potential participants will be sent an introductory letter and a patient information sheet. The introductory letter will briefly describe the study and include a local or toll free number to call if the patient is not interested in participating or would like more information. After one week, a study coordinator will telephone those Veterans who did not opt-out, and if the patient is interested, the coordinator will ensure the patient is properly informed, obtain verbal informed consent, administer the Brief Screener by phone and determine whether that Veteran meets the criteria of having a clinically meaningful symptom burden score (1 or higher on any one symptom, as a measure of low function or high symptom burden) on at least one item.

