5.6 Data Analysis

- **Provide sample size determination and analysis (include anticipated rate of screen failures, study discontinuations, lost to follow-up etc.).**

In a recent EPIC study, the minimal clinically important difference for the four EPIC domains was defined as the difference in scores between patients who were completely satisfied with their symptom burden (function and bother combined) versus only somewhat satisfied. Minimally important differences ranged from 0.33 standard deviation (SD) to 0.5 SD, which translated into a difference of six points for urinary incontinence scores, four points for bowel, 10 points for sexual function, and 4 points for hormonal symptoms. In the proposed study, we consider these differences as the clinically meaningful between-group mean difference in symptom reduction. To detect a 0.33 SD difference in symptom reduction between patients receiving the automated PC symptom support versus standard information at 12

month with 90% power, we will need 394 participants (197 per group), based on using a regression analysis adjusting for baseline values (analysis of covariance) with an α of 0.0125 with 0.5 as an assumed correlation between baseline and follow-up symptom scores. Note that the α value was chosen conservatively to detect symptom reduction in any of the four domains. The power will be higher to detect a larger than 0.33 SD between-group difference in symptom reduction and also to detect the same difference with higher correlation than 0.5 between baseline and follow-up symptom values. Assuming conservatively 15% attrition at each assessment time, we propose to enroll 550 participants in total with an anticipated 397 participants to complete assessments at the second assessment time. The number of eligible prostate cancer patients at each site is sufficient for recruitment. For interval scale outcomes measures such as confidence in symptom self-management, the proposed sample size should give adequate power to detect at least 0.33 SD differences between groups.

- **Describe how, where and by whom the data will be analyzed.**

All data will be analyzed at the Ann Arbor VA. The qualitative data analyst, [name], the data manager, [name], and Drs. [name], [name] and [name] will participate in the data analysis.

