Aim 1 outcome analyses: Our primary outcomes for Aim 1 will be changes in symptom burden and bother scores at 5-months relative to baseline, using the EPIC measure. We will also evaluate these outcomes at the 12-month assessment point, but focus on the 5-month for primary outcome assessment as it is closest to the completion of the intervention. Multiple regression analysis will be used to evaluate the primary outcomes. The model will include an indicator for intervention group as the primary independent variable, and treatment type indicator (surgery vs. radiotherapy) and study site indicators as covariates. Baseline variables found to differ between the two study groups in the baseline analysis will also be included as covariates, though we expect the groups to be balanced on demographic and symptom scores by the randomization process. The coefficient for the intervention group indicator will be used to evaluate the impact of the personalized automated prostate cancer symptom management program compared to standard information. For change in symptom burden, we will repeat the analysis using each of the four symptom domains for EPIC. We will use the same analytic approach to evaluate changes in confidence in symptom self-management, our second Aim 1 outcome. We hypothesize that for both Aim 1 outcomes, intervention group survivors will have better scores at both 5- and 12-month assessments relative to those in the group (i.e., less symptom burden and better PC-QOL, more confidence in symptom self-management). For patients with available data at both 5- and 12-months, we will assess the trajectory of symptoms over time. This will be done using a linear mixed-effects model with random effects for each subject, an indicator for intervention group, an indicator of follow-up wave (5 versus 12 months) and an interaction of time by intervention group to model potential changes in the intervention effect on symptoms soon (at 5-months) vs. long (at 12-months) after the intervention is discontinued. If the interaction is not significant, we will drop the interaction term from the model and estimate the time-averaged difference in outcomes between the two study groups. Analyses of other outcomes, such as self-management implementation and confidence, will be done similarly.

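### The secondary 5-versus-12-month mixed model is limited to men with both follow-up scores, which leaves out about 70 men whose 5-month score it could use

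*Combined protocol and SAP*

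**What the plan says.** All of this is in Section 5.6 (Data Analysis) of the combined protocol and SAP unless stated otherwise.

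- **Primary analysis.** Under the Aim 1 outcome analyses, the primary outcome is change in EPIC scores at 5 months, analysed by multiple regression. The investigators "focus on the 5-month for primary outcome assessment as it is closest to the completion of the intervention". The same outcomes are also evaluated at 12 months. Neither analysis is limited to men with both follow-ups.
- **Trajectory model.** "For patients with available data at both 5- and 12-months, we will assess the trajectory of symptoms over time". The next sentence attaches that set to a specific model: "This will be done using a linear mixed-effects model with random effects for each subject, an indicator for intervention group", with follow-up wave and a group-by-time interaction. If the interaction is not significant it is dropped, and the model is used to "estimate the time-averaged difference in outcomes between the two study groups".
- **Other outcomes.** "Analyses of other outcomes, such as self-management implementation and confidence, will be done similarly".
- **Attrition and numbers.** "Assuming conservatively 15% attrition at each assessment time, we propose to enroll 550 participants in total with an anticipated 397 participants to complete" the second assessment. Section 5.2 (Recruitment Methods) gives a different number randomised: "We estimate as many as 553 - 650 veterans will be randomized".
- **Sample size.** The calculation is "based on using a regression analysis adjusting for baseline values (analysis of covariance"), with a baseline-to-follow-up correlation of 0.5.

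The documents give no method for missing outcomes in the trajectory model and no sensitivity analysis that would bring back men with one follow-up. By contrast, the Aim 2 logistic model is stated to include all participants.

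**The concern.** A mixed model is usually chosen for repeated measures because it accepts incomplete records. A man with only a 5-month score informs the 5-month contrast directly. Through the within-man correlation he also informs the 12-month contrast. Limiting the model to men with both scores gives up that advantage.

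Two things follow. The model loses information that has already been collected. And the analysis set is defined by what happens after randomisation, so its estimates describe a smaller group than the primary 5-month regression does and need a stronger assumption than missing at random given the observed scores. At stake are the test of whether the effect changes between 5 and 12 months and, if that test is not significant, the time-averaged difference.

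**Working it through.** **Inputs from Section 5.6.** 550 enrolled; 15% attrition at each assessment; effect 0.33 SD; alpha 0.0125; power 90%; baseline-to-follow-up correlation 0.5.

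**Inputs assumed.** Drop-out is monotone (nobody misses 5 months and returns at 12). The between-wave correlation *r*, before baseline adjustment, is 0.4 to 0.7. The documents give neither.

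**Step 1: reproduce the plan's figures.** Residual variance after baseline adjustment is 1 − 0.5² = 0.75. Two-sided, the number per arm is 2 × 0.75 × (2.498 + 1.282)² / 0.33² = 196.7, so 197 per group and 394 in total, as stated. Completers: 550 × 0.85² = 397.4, matching 397.

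**Step 2: count the men left out.** With a 5-month score: 550 × 0.85 = 467.5. With a 5-month score only: 467.5 − 397.4 = 70.1. If 553 are randomised: 553 × 0.85 × 0.15 = 70.5. If 650: 650 × 0.85 × 0.15 = 82.9. The range is therefore 71 to 83.

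**Step 3: put the correlation on one scale.** After baseline adjustment, the between-wave correlation is *a* = (*r* − 0.25)/0.75. So *r* of 0.4 to 0.7 becomes *a* of 0.2 to 0.6.

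**Step 4: precision.** Per arm, *n* = 198.5 men have both scores and *m* = 35 have a 5-month score only, so *m*/(*n* + *m*) = 0.150.

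- Time-averaged difference: information per arm is 2*n*/[0.75(1 + *a*)] for both-waves men, plus *m*/0.75 if the others are added. SE = √(2/information).
- 12-month difference: variance ratio, all men to both-waves men, is 1 − *a*² × 0.150.
- Interaction: variance ratio is 1 − ½(1 − *a*) × 0.150.

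| *r* | *a* | SE of average, both waves (SD) | SE of average, all men (SD) | Fall, average | Fall, 12-month | Fall, interaction |
|---|---|---|---|---|---|---|
| 0.4 | 0.20 | 0.067 | 0.064 | 4.9% | 0.3% | 3.0% |
| 0.5 | 0.33 | 0.071 | 0.067 | 5.4% | 0.8% | 2.5% |
| 0.6 | 0.47 | 0.074 | 0.070 | 5.9% | 1.6% | 2.0% |
| 0.7 | 0.60 | 0.078 | 0.073 | 6.4% | 2.7% | 1.5% |

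For example, at *r* = 0.4 the information is 397/0.90 = 441.1, so SE = √(2/441.1) = 0.0673. Adding 35/0.75 = 46.7 gives 487.8 and SE = 0.0640.

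**Step 5: relax monotone drop-out.** Section 5.7 ends contact only with men who say they no longer wish to continue, so a man who misses 5 months can return at 12. If 15% missed each wave independently, another 550 × 0.15 × 0.85 = 70.1 men would have a 12-month score only, and they would also be left out. The count of 70 would then be too low.

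**The case against.** The strongest reply is that the consequences are small. The model's stated purpose is to examine change in the effect between waves, and the interaction gains only 1.5-3%. The larger gain falls on the time-averaged difference, which is estimated only if the interaction is not significant. The effect at each wave is also evaluated separately, without this limit. All of that stands, and it is why the point is minor.

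It may also be said that a trajectory needs two points. That is true of one man's change. The model's results, however, are differences between groups at each wave and their average, and a single score informs these.

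Three stronger readings are tempting, and the documents do not support them:

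- **That the primary result loses these men.** It does not. The 5-month regression can use their 5-month scores.
- **That the trajectory results are biased.** Bias arises only if later drop-out depends on outcome differently in the two arms, and nothing in the documents shows this. In an invented case (drop-out tied to the 5-month score in one arm only, log-odds slope 0.5 per SD, *r* = 0.6), the false change between waves is about 0.03 SD. The interaction SE is √(4(1 − *r*)/198.5), or 0.078 to 0.110 for *r* of 0.7 to 0.4. With equal slopes in both arms there is no bias.
- **That self-management implementation and confidence certainly carry the same limit.** The plan says only that they are handled similarly, which leaves the analysis set open.

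**Conclusion.** The point holds, as a minor one. The plan limits a secondary mixed model to men with both follow-ups, for no stated reason and with no provision for the rest. About 70 of 467 men with a usable 5-month score are set aside (71 to 83 if 553 to 650 are randomised). That count is derived from the plan's 15% attrition and rests on monotone drop-out; men who return at 12 months would add to it. The precision lost is about 5-6% of the SE for the time-averaged difference and at most about 3% for the 12-month difference and the interaction. These figures rest on an assumed unadjusted between-wave correlation of 0.4 to 0.7. Only the interaction and the conditional time-averaged estimate are affected. The case for changing the text is that it is nearly free and removes a selection made after randomisation, not that a conclusion of the trial is in danger.

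**What to change.** In the Aim 1 outcome analyses of Section 5.6, replace the opening condition of the trajectory sentence with: *For all randomised participants with at least one follow-up EPIC score*. State that the model is fitted by maximum likelihood. Where other outcomes are analysed with this model, say that the same rule applies with the matching score. Keep the both-waves set as a sensitivity analysis.

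The cost is wording only; data and software are unchanged. The downside is that the main result then relies on missing at random. If drop-out follows the unseen 12-month score, the change removes only part of any bias, and comparison with the both-waves analysis would not settle the matter.

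As separate, optional advice, baseline EPIC could be added as a covariate in this model, in line with the analysis of covariance behind the sample size.

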3.0 Objectives

- **Describe the study's purpose, specific aims, or objectives.**

The specific aims are:

1) To conduct a randomized controlled trial among PC survivors with high symptom burden comparing the impact of this personalized intervention for improving symptoms and symptom self-management to nonpersonalized information. We hypothesize that relative to controls, 5- and 12- months post-enrollment, Veterans in the intervention group will: 1) have higher confidence about symptom self-management; and 2) report lower symptom burden and better disease-specific QOL. We further hypothesize that at the 12-month assessment point, the intervention group will have higher scores on two key psychosocial indicators (subjective health and perceived cancer control) than the control group.

2) To determine the intervention's impact on the use of primary and specialty VA services. We hypothesize that relative to controls, 12 months after enrollment, Veterans in the intervention group will have a higher rate of symptom-specific service use that is consistent with Michigan Cancer Consortium recommendations for prostate cancer survivorship care, which are expert and evidence-based. This project could have a significant positive impact on the lives of the large and growing population of Veterans who are PC survivors experiencing post-treatment symptoms. Data from our preliminary work suggest that many of these survivors continue to suffer with high symptom burden years after treatment, report wanting to participate in self-management interventions, and that an automated telephone system is feasible and potentially effective. Our team has extensive expertise in the development and deployment of highly personalized, automated interventions for improving self-management in the VA, as well as the clinical and health services research expertise to successfully implement and complete the study. We have the support of the Office of Specialty Care/Patient Care Services as well as the VA Ann Arbor PACT (Patient Aligned Care Team) Laboratory. To ensure that the trial has the greatest possible impact on VA care, we will conduct a process evaluation to determine how the intervention can best optimize the quality of life and survivorship care for Veterans with prostate cancer and inform program implementation with our primary care partners.

- **State the hypotheses to be tested.**

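### The supporting mixed model drops the arm-by-wave term when it is not significant, so a partial fade between 5 and 12 months can often be replaced by an average that fits neither time point

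*Combined protocol and SAP*

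**What the plan says.** The Aim 1 hypotheses in section 3.0 are stated for both follow-ups: "relative to controls, 5- and 12- months post-enrollment, Veterans in the intervention group will" do better on confidence, symptom burden and disease-specific quality of life.

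Section 5.6 (Aim 1 outcome analyses) plans two layers of analysis.

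- **Time-point regressions.** "Multiple regression analysis will be used to evaluate the primary outcomes", and on timing: "We will also evaluate these outcomes at the 12-month assessment point, but focus on the 5-month for primary outcome assessment". The symptom analysis is repeated for each of the four EPIC domains.
- **A longitudinal model.** "For patients with available data at both 5- and 12-months, we will assess the trajectory of symptoms over time". This is a linear mixed model with arm, wave and "an interaction of time by intervention group to model potential changes in the intervention effect on symptoms soon (at 5-months) vs. long (at 12-months", that is, shortly after and long after the intervention has stopped. The rule follows: "If the interaction is not significant, we will drop the interaction term from the model and estimate the time-averaged difference in outcomes". Other outcomes, including implementation of self-management and confidence, are to be handled in the same way.

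No significance level and no power are given for the interaction test. The sample size paragraph of section 5.6 concerns one contrast only: "To detect a 0.33 SD difference in symptom reduction between patients receiving the automated PC symptom support versus standard information at 12" months.

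**The concern.** The mixed model is there to show whether the 5-month effect lasts to 12 months. Section 5.5 describes four automated calls over three months, so the last assessment comes about nine months after the calls end, and some fading is a realistic possibility. It is the only planned formal comparison of the two effects; the separate regressions give no interval for the change between them.

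Under the rule, a p-value decides which quantity this model delivers. A non-significant interaction may mean that the effects are alike, or only that the test could not tell them apart. In either case the two time-specific effects are replaced by their average, which answers neither the 5-month nor the 12-month hypothesis. If the rule is applied outcome by outcome, which is a natural reading although not spelled out, the mixed-model results could appear per time point for some EPIC domains and as an average for others.

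**Working it through.** **1. The plan's own figures.** Inputs from section 5.6: 0.33 SD, 90% power, α = 0.0125 (two-sided reproduces the plan), baseline correlation 0.5.

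n per arm = 2 × (2.498 + 1.282)² × (1 − 0.5²) / 0.33² = 196.7, so 197 per arm and 394 in total, as stated. Completers: 550 × 0.85² = 397.4, as stated (397). The sample size is sound for a single contrast.

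**2. Precision of the interaction.** Assumptions: the 397 men have both follow-ups, allocation is equal, SDs are equal at the two waves, and r is the correlation between the 5- and 12-month scores. The documents do not give r, so 0.5 to 0.8 is shown.

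- SE of the arm difference at one wave = 2/√397 = 0.1004 SD.
- SE of the difference between the two arm effects = 0.1004 × √(2(1 − r)) = 0.1004 (r = 0.5), 0.0898 (0.6), 0.0778 (0.7), 0.0635 (0.8).
- Baseline adjustment does not change these: the baseline contribution cancels in the within-person difference.

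**3. How often the term is dropped.** For a fade δ tested two-sided at 0.05, P(drop) = Φ(1.96 − δ/SE) − Φ(−1.96 − δ/SE). Example, half fade with r = 0.5: δ/SE = 0.165/0.1004 = 1.644, and Φ(0.316) − Φ(−3.604) = 0.624.

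With 0.33 SD at 5 months:

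| True 12-month effect (SD) | Average of the two (SD) | r = 0.5 | r = 0.6 | r = 0.7 | r = 0.8 |
|---|---|---|---|---|---|
| 0.22 (one-third fade) | 0.275 | 80.5% | 76.8% | 70.7% | 59.0% |
| 0.165 (half fade) | 0.2475 | 62.4% | 54.9% | 43.6% | 26.1% |
| 0.11 (two-thirds fade) | 0.22 | 40.8% | 31.2% | 19.2% | 6.6% |
| 0 (complete fade) | 0.165 | 9.2% | 4.3% | 1.1% | 0.1% |

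The fade detectable with 80% power is (1.96 + 0.84) × SE, or 0.28 SD at r = 0.5 and 0.18 SD at r = 0.8. If the interaction were tested at 0.0125 instead, the half-fade drop rates would be 80% to 46%, and the complete-fade rate at r = 0.5 would be about 21%.

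**4. What is reported when the term is dropped.** The average is (0.33 + d12)/2, where d12 is the true 12-month effect. For a half fade it is 0.2475 SD: 50% above the 12-month effect (0.2475/0.165 = 1.5) and 25% below the 5-month effect (0.2475/0.33 = 0.75). With equal SDs the average and the difference are independent, so selecting on a non-significant test does not move the expected average.

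**5. If the pooled interval were read as a 12-month interval.** SE of the average = 0.1004 × √((1 + r)/2) = 0.087 (r = 0.5) to 0.095 (r = 0.8). For a half fade, its 95% interval would cover the true 12-month effect 84% to 86% of the time. With baseline adjustment at the plan's correlation of 0.5, coverage is about 79% at r = 0.5 and 81% at r = 0.7.

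**The case against.** The strongest reply is that the 12-month effect does not depend on this model. Section 5.6 makes the 5-month regression primary, also evaluates 12 months, and repeats the symptom analysis by domain. It further plans the percentage of men above an EPIC score of 70 at both follow-ups and graphs over time by arm. This stands. A reader might infer that the pre-test decides what the trial reports at 5 or 12 months, or that the primary result is compromised. The documents do not support that: both time-specific regressions are done whatever the interaction shows.

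A reader might also infer that any fading effect will probably be hidden. That is too strong. From 0.33 SD, a complete fade is detected in about 91% or more of trials at 0.05. A half fade is missed more often than not only when r is below about 0.65, and a two-thirds fade is caught more often than missed at every r shown.

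Nor is the pooled figure biased for what the plan calls it. It is a fair estimate of the average, and it errs against the intervention at 5 months as much as for it at 12. The coverage figures above show harm only if the interval is read as a 12-month result. Nor does anything bar the team from reporting the interaction estimate before dropping the term.

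What remains is that the plan does not require that estimate to be reported, and the separate regressions do not supply it. An inconclusive test thus removes the model's estimate of change, and the resulting average may sit awkwardly beside the 12-month regression with no stated order of precedence.

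**Conclusion.** The point holds for the supporting mixed model and for partial fading. The rule lets a test that the trial was not sized for choose which quantity that model reports. The size depends on two things the documents do not fix, r and the significance level of the interaction test, and on a 5-month effect of 0.33 SD. A smaller 5-month effect would make the same proportional fade harder to detect.

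The harm is confined to the trajectory model and to the other outcomes analysed in the same way. The primary 5-month analysis, the separate 12-month analysis and the sample size stand. This is a worthwhile, inexpensive improvement and not a threat to the trial's main conclusion.

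**What to change.** In section 5.6, delete the rule that drops the interaction. State instead that arm-by-wave stays in the mixed model whatever its p-value, and that for every outcome analysed this way the report gives the 5-month effect, the 12-month effect and their difference, each with a confidence interval. The time-averaged difference may be added as a summary but must not replace them.

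This changes one sentence and needs no extra participants or data: 197 per arm already gives 90% power for 0.33 SD at 12 months on the plan's assumptions. The cost is precision. Each time-specific interval is wider than the pooled one by a factor of √(2/(1 + r)) before baseline adjustment, or about 15% at r = 0.5 and 5% at r = 0.8.
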